15.5 Vital Signs

Population: SAF analysis set

The following vital signs parameters data from "Vital Signs" eCRF pages will be considered:

- Systolic and diastolic blood pressure
- Pulse rate
- Body temperature
- Respiratory rate
- Weight

One figure for each dose level will be produced, with six spider plots (one for each parameter) in the same page using panel layout. On each plot, one curve per subject will display the absolute value against the treatment day.

Additionally, a listing will be produced, including: dose level, subject ID, age, sex, race, first and last M3541/RT administration date and number of fraction days, parameter (unit), visit, date of collection and relative day, value, details of collection method, change from baseline and baseline flag.

15.6 ECOG Performance Status

Population: SAF analysis set

The listing will include all the data from the "ECOG Performance Status" eCRF section.

Additionally, one spaghetti plot per dose level will be produced, using different colors per patient.

15.7 ECG and QT/QTc evaluations

Population: SAF analysis set

Electrocardiogram values based on "Electrocardiogram" eCRF page will be used for summary statistics and shift tables.

Time of ECG collection will be expressed both as actual and nominal (i.e. expected) time elapsed from first M3541 administration in hours, derived as defined at section 9. The following spider graphs will be produced separately using actual and nominal times for QTcF, as collected in the eCRF. Three. Three plots per dose level will be produced, with one curve per subject according to the specifications below:

- 1. Overall: Time point (in hours) on the x-axis (From -1 to 250) vs. QTcF observed value on the y-axis (i.e. results collected 72 and 240 hours post fraction 9 dose will not be presented)
- 2. Fraction Day 1: Time point (in hours) on the x-axis (From -1 to 12) vs. QTcF observed value on the y-axis
- 3. Fraction Day 9: Time point (in hours) on the x-axis (From 240 to 250) vs. QTcF observed value on the y-axis.

ECG parameters on-treatment will be presented by the following frequency table (by dose level and overall):

- Shift from normal baseline result to any abnormal post-baseline result (i.e. maximal ontreatment value)
- Worst absolute QTcF interval post-baseline
 - \circ > 450 ms and \leq 480 ms
 - \circ > 480 ms and <500 ms
 - \circ > 500 ms
- Worst QTcF increase from baseline
 - \circ > 30 ms and < 60 ms
 - o > 60 ms

Two listings will display all the results as presented in "ECG" eCRF page, one on Qualitative Results (rhythm and ECG interpretation) and another one on Quantitative Results (heart rate, PQ/PR duration, RR duration, QRS duration, QT duration, QTcF). All visits and time points will be included in listings.

One additional listing will contain all the information from the "Continuous Holter" eCRF page.

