#### 5.3.2 Exclusion Criteria

Subjects are not eligible for this study if they fulfill any of the following exclusion criteria:

- 1. Use of other anticancer therapy (see Section 6.5.2) within 5 x their elimination half-life, but no longer than 15 days, before the first dose of M3541 administration. The use of any investigational agent is not allowed within 28 days before the first dose of M3541
- 2. Residual toxicity due to previous anticancer therapy with no return to baseline or Grade  $\leq 1$  (except alopecia) according to CTCAE V4.03
- 3. Extensive prior RT on more than 30% of bone marrow reserves (by Investigator judgment), or prior bone marrow / stem cell transplantation within 5 years before study start
- 4. Prior RT to the same region that would be irradiated in this study
- 5. Subjects at increased risk for radiation toxicities, such as known collagen vascular disease (eg, scleroderma, Sjogren's disease, etc) or other inherited radiation hypersensitivity syndromes (eg, Gorlin syndrome, Fanconi anemia, ataxia-telangiectasia, etc.)
- 6. Major surgical intervention within 28 days prior to the first dose of M3541 administration

- Significant cardiac conduction abnormalities, including a history of long corrected QT interval (QTc) syndrome and / or pacemaker, or impaired cardiovascular function such as New York Heart Association classification score > 2
- 8. Hypertension uncontrolled by medication
- 9. Known central nervous system (CNS) metastases causing clinical symptoms or metastases that require therapeutic intervention. Subjects with a history of treated CNS metastases (by surgery or radiation therapy) are not eligible unless they have fully recovered from treatment, demonstrated no progression for at least 2 months, and do not require continued steroid therapy. Subjects with CNS metastases incidentally detected during Screening that do not cause clinical symptoms and for which standard of care suggests no therapeutic intervention is indicated, should be discussed with the Sponsor Medical Responsible

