#### 7.2.6 Cardiac Assessments

A 12-lead ECG will be recorded at Screening. The ECG will be recorded after the subject has been in a supine position breathing quietly for 5 minutes and prior to any associated PK blood sampling. The ECG should be obtained using a Holter recorder. The ECG results will be used to evaluate the heart rate, atrial-ventricular conduction, QR, QT, and QTc intervals, and possible arrhythmias. All ECG and ECG extract results must be reviewed at the site by the Investigator or a medically qualified designee for clinical management of the subject.

The Investigator will judge the overall ECG interpretation as normal or abnormal. If abnormal, it will be decided if the abnormality is clinically significant or not clinically significant and the abnormality will be recorded on the eCRF. Any clinically significant ECG abnormality (cardiac assessment) will be recorded as an AE or SAE as appropriate (see Section 7.4.1 and subsections).

In presence of a Grade  $\geq$  3 QTc prolongation (QTc  $\geq$  501 ms and / or an increase with at least 60 ms over baseline, on 2 separate consecutive ECGs that cannot be explained by the underlying medical condition or concomitant therapy) the treatment with M3541 should be interrupted and the subject evaluated by a cardiologist. The IMP M3541 will be re-introduced only after recovery of QTc to  $\leq$  480 ms (Grade 1) if recovery is within 3 days and the QTc prolongation was deemed unrelated to M3541. In case of incomplete recovery (QTc between 480 and 500 ms) and in the presence of demonstrated clinical benefit to the subject, described as CR, PR, or a minor response (minor response being a regression of at least 20%), M3541 may be re-introduced if the QTc prolongation was deemed unrelated to M3541 and upon agreement with the cardiologist and in consultation with the Sponsor, and with the agreed expectation that the clinical benefit of resuming M3541 treatment with RT is greater than the potential risk.

Document No. CC

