8.2 Definition of Analysis Sets and Subgroups

Screened Analysis Set (SCR):

The SCR will include all the subjects who signed the informed consent form (ICF).

Safety Analysis Set (SAF):

The SAF will include all subjects who received at least 1 dose of M3541. Subjects will be analyzed according to the actual treatment (i.e., dose level as collected in the "Cohort" eCRF page) they received.

Dose Limiting Toxicity Analysis Set (DLT):

The DLT analysis set will include all subjects who received at least 1 dose of M3541 and meet at least 1 of the following criteria:

- Experienced at least 1 DLT during the DLT evaluation period as defined in section 9, regardless of the number of doses of M3541 administered
- Received at least 80% of planned dose of each treatment, i.e. 8 fractions of RT and 8 of 10 M3541 administrations, and completed the DLT evaluation period (i.e. provided at least one safety result on or after the end date of the period, as defined at section 9).

Pharmacokinetics Analysis Set (PKS):

The PKS analysis set will consist of all subjects who received at least one dose of M3541, and provided at least one quantifiable postdose concentration.

Postdose data for a fraction day from subjects with a vomiting episode within 2 times of t_{max} time of M3541 (vomiting at around 4 hours postdose) or any other significant event affecting PK may be excluded from final PK analysis on a case-by-case basis. Subjects will be analyzed according to the actual treatment (i.e., dose level as collected in the "Cohort" eCRF page) they received. All PK analyses will be based on this analysis set.

Biomarker Analysis Set (BMK):

The Biomarker (BMK) analysis set will consist of all subjects who received at least 1 dose of M3541 and have provided a quantifiable blood sample for pharmacodynamic/biomarker analysis prior to any M3541 treatment and at least 1 quantifiable post-treatment blood sample. Subjects will be analyzed according to the actual treatment (i.e., dose level as collected in the "Cohort"

eCRF page) they receive. All pharmacodynamics and biomarker analyses will be based on this analysis set.

Table 3: Summary of analyses and associated analysis set

Analyses	SCR	SAF	DLT	вмк	PKS
Dispositions and deaths	✓				
Baseline Assessments		✓			
Past and Concomitant Therapies		✓			
Compliance and Exposure		✓			
Primary endpoint: DLTs			✓		
Efficacy endpoints		✓			
Safety and tolerability		✓			
Biomarkers and pharmacodynamics				✓	
Pharmacokinetics					✓

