9 General Specifications for Data Analyses

Posterior distribution and recommended next dose level will be calculated using EAST Version 6.4 or higher.

Non-compartmental computation of PK parameters will be performed using Phoenix WinNonlin Version 6.4, or higher.

All other statistical analyses will be performed using SAS Version 9.2 or higher, or R, Version 3.0.2 or higher.

Pharmacokinetic figures will be prepared using SigmaPlot Version 12.5 or higher or SAS Version 9.2 or higher.

Data handling after cut-off date for SMC and primary analyses:

Data after cut-off for SMC and primary analyses do not undergo the cleaning process. Hence data obtained after the cut-off will not be displayed in listings or used for summary statistics (e.g. laboratory values of samples taken after data cut-off, AE with onset date after data cut-off, etc.).

Presentation of continuous and qualitative variables:

Data will be presented by dose level and overall unless specified otherwise. The dose level will be defined by the planned dose of the corresponding cohort. If several cohorts have same dose level, they will be pooled together for all summary outputs.

Continuous variables will be summarized using descriptive statistics, i.e.

• Number and percentage of subjects, number and percentage of subjects with missing values

- Mean, 95% confidence intervals (CI), as appropriate
- Standard deviation (SD)
- Median
- Q1, and Q3
- Minimum (Min), and maximum (Max)

Mean, median, Q1, Q3, Min, and Max will have the same precision as collected in SDTM datasets for non-derived data. Standard deviation will be presented with 1 digit more than the mean. For derived data, the number of decimal digits will be defined on a case-by-case basis.

Missing statistics, e.g., when they cannot be calculated, should be presented as "nd". For example, if n=1, the standard deviation cannot be computed and should be presented as "nd".

Qualitative variables will be summarized by frequencies and percentages.

Unless otherwise stated, the calculation of proportions will be based on the number of subjects of the analysis set of interest. Therefore, counts of missing observations will be included in the denominator and presented as a separate category.

If there are no missing values, this should be indicated by a 0 (0.0).

In case the analysis refers only to certain visits, percentages will be based on the number of subjects still present in the trial at that visit, unless otherwise specified.

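### The ECG table in SAP 15.7 has no baseline-by-worst cross-tabulation, so its shift percentage lacks an at-risk denominator and its absolute QTcF bands mix pre-existing with new values

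*SAP*

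**What the plan says.** SAP 15.7 (ECG and QT/QTc evaluations) uses the SAF and defines one frequency table, by dose level and overall, with three blocks:

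- "Shift from normal baseline result to any abnormal post-baseline result"
- "Worst absolute QTcF interval post-baseline", in bands that begin above 450 ms
- "Worst QTcF increase from baseline", in bands that begin above 30 ms

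SAP 8.2 defines the population: "The SAF will include all subjects who received at least 1 dose of M3541". No baseline or post-baseline ECG is required. SAP section 9 sets the default denominator: "Unless otherwise stated, the calculation of proportions will be based on the number of subjects of the analysis set of interest". It adds that missing observations stay in the denominator as a category of their own. Section 15.7 states no exception.

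On eligibility, the cardiac criterion in Protocol 5.3.2 excludes significant conduction abnormalities, "including a history of long corrected QT interval (QTc) syndrome", but the entry criteria set no numeric QTc ceiling.

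For hematology and chemistry, SAP 15.4 specifies a full cross-tabulation of baseline by worst on-treatment category, with Missing and Total, restricted to subjects with post-baseline values. SAP 15.7 gives no equivalent for ECG, although it says that ECG values will feed shift tables. Protocol 8.5.4.3 plans changes from baseline for ECG.

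**The concern.** ECG abnormality, including QTc, is a named secondary safety endpoint (Protocol 8.3.2). The table gives a percentage for new abnormality, and a reader will compare it across dose levels. Two features weaken that comparison.

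First, a subject whose ECG is already abnormal at baseline cannot satisfy the shift row but still counts in its denominator. The percentage falls as the share of such subjects rises, whatever the drug does. With about 3 subjects per dose level, chance imbalance in baseline ECGs can create or hide an apparent dose pattern.

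Second, the absolute QTcF bands record the worst post-baseline value without reference to where the subject started. A stable value above 450 ms that was present at entry falls in the same cell as a new crossing of 450 ms.

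**Working it through.** The plan states no numerical figure for this table, so there is none to reproduce. The check applies the table's own rules to examples.

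**Inputs.** Population and denominator: SAP 8.2 and section 9. Rows: SAP 15.7. Planned cohort size of 3: Protocol 8.1. Maximum of 30 evaluable subjects: Protocol 5.1.1. The share of subjects abnormal at baseline is not in the documents, so it is varied below as an assumption.

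**1. Shift row.** Let N be the SAF subjects at a dose level, a the number abnormal at baseline, and p the rate of new abnormality among those normal at baseline. Assume for simplicity that everyone has a baseline and a post-baseline ECG.

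Reported rate = p × (N − a) / N

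Take N = 30 and assume p = 20%:

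| Abnormal at baseline (a) | At risk (N − a) | Reported, SAF denominator | Normal-baseline denominator |
|---|---|---|---|
| 3 | 27 | 18.0% | 20.0% |
| 6 | 24 | 16.0% | 20.0% |
| 9 | 21 | 14.0% | 20.0% |
| 12 | 18 | 12.0% | 20.0% |
| 15 | 15 | 10.0% | 20.0% |

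Subjects without a post-baseline ECG reduce the reported rate in the same way.

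For one cohort of 3, the row's ceiling is (3 − a)/3: 66.7% with one subject abnormal at baseline and 33.3% with two. If every at-risk subject shifts at two dose levels, one with a = 0 and one with a = 1, the table shows 3/3 = 100% and 2/3 = 66.7%. The at-risk rates are identical (3/3 and 2/2).

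**2. Absolute QTcF bands.** Example subjects classified by the rules of SAP 15.7:

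| Baseline → worst (ms) | Rise (ms) | Absolute band | Increase band |
|---|---|---|---|
| 460 → 462 | 2 | >450 to ≤480 | none |
| 440 → 455 | 15 | >450 to ≤480 | none |
| 430 → 465 | 35 | >450 to ≤480 | >30 to <60 |
| 460 → 448 | −12 | none | none |

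The first two subjects are indistinguishable in the table, although one entered above 450 ms and the other crossed it on treatment. The increase block does mark the third subject as different, but only as a separate count.

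**3. Why separate counts are not enough.** Take two pairs of subjects:

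- Pair A: 430 → 465 (rise 35) and 410 → 415 (rise 5).
- Pair B: 460 → 462 (rise 2) and 400 → 435 (rise 35).

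Each pair gives one subject in the >450 to ≤480 band and one in the >30 to <60 band. In pair A one subject newly crossed 450 ms with a rise above 30 ms. In pair B nobody crossed. The two blocks read the same for both pairs.

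**The case against.** **The table already uses baseline.** A reader might infer that it ignores baseline status. It does not: the shift row is conditional on a normal baseline, and the third block is an increase from baseline. A reader might also infer that a high entry value is reported as drug-induced prolongation. The row is labelled as an absolute post-baseline interval, and a subject enters it only if a post-baseline value also exceeds 450 ms (460 → 448 ms is not counted). What stands is narrower: a missing at-risk denominator and a missing cross-tabulation.

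**The denominator is inferred.** It comes from a default that allows exceptions, and SAP section 18 places the table specifications in a separate document that is not available here. This is fair, and the dilution is conditional on those shells. The SAP itself states no exception.

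**Clinically significant worsening is captured elsewhere.** A reader might infer that a change from an insignificant to a significant abnormality is lost. Protocol 7.2.6 requires clinically significant ECG abnormalities to be recorded as AEs or SAEs, and SAP 15.2 counts onset or worsening as a TEAE. That answers the inference. Nor do the documents show that significance is a coded field: Protocol 7.2.6 says "it will be decided if the abnormality is clinically significant or not clinically significant" and that the abnormality goes on the eCRF, while SAP 15.7 lists only rhythm and interpretation.

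**Trivial readings.** Protocol Table 4 schedules 24 mandatory ECGs after the first dose (7 + 8 + 8 + 1), so a reader might infer that most subjects will show a shift by chance. Any such percentage needs a per-reading probability, which the documents do not give, and independence within subject, which is implausible for several readings within six hours. No figure is claimed.

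**The row is ambiguous.** Its gloss about a maximal value could mean that it concerns quantitative parameters rather than the overall interpretation. The denominator point holds on either reading.

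**Impact is limited.** All ECG results are listed, QTcF plots start at screening, and with about 3 subjects per dose level individual courses can be read directly. This stands and limits the weight of the point, but it does not correct the tabulated percentage.

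**Conclusion.** The point holds in limited form. As the SAP is written, the shift percentage is the at-risk rate multiplied by the share at risk. Over the assumed range of 10% to 50% abnormal at baseline, a 20% at-risk rate is reported as 18.0% down to 10.0%. A dose level of 3 is capped at 66.7% or 33.3% when one or two subjects start abnormal. This rests on the section 9 default not being overridden in the table shells and on baseline shares that the documents do not supply.

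The absolute QTcF bands cannot separate a value already above 450 ms at entry from a new crossing with a rise of 30 ms or less. That follows from the row definitions and needs only that entry above 450 ms is possible, which the eligibility criteria allow.

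A reader might go further and infer that the dose decision is at risk. It is not: MTD determination rests on DLTs in the DLT Analysis Set. This is a descriptive secondary safety table, and the change is an inexpensive improvement.

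**What to change.** In SAP 15.7:

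1. Replace the shift row with a table of baseline ECG result (normal / abnormal / missing) by worst on-treatment result, following the pattern in SAP 15.4. Base percentages on subjects in each baseline category with at least one post-baseline ECG. Split abnormal by clinical significance only if the eCRF codes it.
2. State whether the row uses the overall interpretation or quantitative parameters, and define worst accordingly.
3. Cross-tabulate worst post-baseline QTcF category, adding a ≤450 ms category, by baseline QTcF category. Keep the increase-from-baseline block.
4. If the table shells already set an at-risk denominator, say so in the SAP.

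The cost is SAP wording and one revised table shell. The core change needs no apparent new data collection. The drawback is small cells: with 3 subjects per dose level many percentages will be 0/1 or 1/1, so counts should be shown with their denominators and the overall column will be the most readable.

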## 8.5.4.3 Physical Examination, Including Vital Signs, 12-lead Electrocardiogram, and Performance Status

Vital signs (body temperature, respiratory rate, pulse, and blood pressure), 12-lead ECG, and ECOG PS recorded according to the Schedule of Assessments (Table 1) will be presented. Each parameter will be summarized by descriptive statistics per time point, and changes from baseline will be calculated.

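### SAP 15.7 specifies no per-time-point, change-from-baseline ECG summary as planned in Protocol 8.5.4.3, and its printed QTcF categories leave exactly 500 ms and exactly +60 ms unclassified

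*SAP*

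**What the plan says.** **Protocol.** Section 8.5.4.3 covers vital signs, 12-lead ECG and ECOG performance status together: "Each parameter will be summarized by descriptive statistics per time point, and changes from baseline will be calculated". Section 8.3.2 lists abnormal ECGs, including the QTc interval, among the secondary endpoints. Section 7.2.6 sets a numeric QTc threshold of at least "501 ms and / or an increase with at least 60 ms over baseline, on 2 separate consecutive ECGs", not explained by the underlying condition or concomitant therapy. When it is met, "the treatment with M3541 should be interrupted and the subject evaluated by a cardiologist".

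**SAP.** Section 15.7 opens with a general statement: "Electrocardiogram values based on 'Electrocardiogram' eCRF page will be used for summary statistics and shift tables". It then specifies:

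- spider plots of observed QTcF, by actual and by nominal time;
- one frequency table by dose level and overall, showing the shift from normal to abnormal, the worst post-baseline QTcF and the worst QTcF increase;
- qualitative, quantitative and Holter listings.

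The absolute QTcF categories are above 450 to at most 480 ms, "> 480 ms and <500 ms", and above 500 ms. The increase categories are "> 30 ms and < 60 ms" and above 60 ms.

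For vital signs, section 15.5 gives plots of absolute values and a listing that includes change from baseline. For ECOG, section 15.6 gives a listing and a plot. Section 7, on changes to the protocol's analyses, mentions only the added pain and interference summaries and the unexplored intermittent schedules.

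**The concern.** A protocol-stated summary of a safety measurement is not specified in the document that is meant to specify it, and no change is declared. A programmer working from SAP 15.7 alone could deliver everything it describes and still not produce what Protocol 8.5.4.3 plans. What would be lost is a display of QTcF, heart rate, PR and QRS by dose and time, with change from baseline. In this plan, ECG change from baseline appears only as each subject's worst QTcF increase.

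The second matter is narrower. A frequency table should place every value in its range in exactly one category. As printed, this one does not, and one of the two omitted values is the increase at which the protocol's numeric threshold begins: "an increase with at least 60 ms over baseline".

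**Working it through.** **1. The planned summary against the specified outputs**

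| Measurement | Protocol 8.5.4.3 | SAP |
|---|---|---|
| 12-lead ECG | Descriptive statistics per time point; change from baseline | 15.7: plots of observed QTcF, shift and worst-value table, listings; the quantitative listing does not name change from baseline |
| Vital signs | Same | 15.5: plots, listing with change from baseline |
| ECOG | Same | 15.6: listing, plot |

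No row contains a per-time-point summary table. Elsewhere the SAP states such summaries outright. Section 16.1.1 summarizes PK concentrations by dose and fraction day, and section 16.2 does so for biomarkers, both observed and as change from baseline. The ingredients for ECG already exist: SAP Table 4 defines the nominal ECG times, and section 9 defines the default statistics for continuous variables.

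The plots do not fill the gap. They stop at 250 h and enlarge Fraction Days 1 and 9, whereas Table 4 puts the end-of-treatment ECG profile for subjects under protocol version 5.0 on Fraction Day 10, at 264 to 270 h.

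**2. Coverage of the categories as printed**

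Every whole value from 451 to 600 ms (absolute) and from 31 to 200 ms (increase) was placed in the printed categories.

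- Absolute: 499 falls in (480, 500) and 501 falls in >500; **500 falls in neither**.
- Increase: 59 falls in (30, 60) and 61 falls in >60; **60 falls in neither**.

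These are the only unclassified values. Repeating the check in steps of 1/3 ms, as for a mean of three readings, gives the same two.

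**3. Against the numeric threshold in Protocol 7.2.6 (QTc ≥ 501 ms and/or increase ≥ 60 ms)**

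- An increase of exactly 60 ms meets it but is uncounted in the SAP table.
- A QTc of exactly 500 ms, with an increase below 60 ms, does not meet it but is also uncounted.

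With categories >480 to ≤500 and >500 ms, and >30 to <60 and ≥60 ms, every tested whole value falls in exactly one category. For whole milliseconds, >500 is then the same as ≥501.

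**4. Precision of the added means**

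The 95% half-width for a mean change at one time point is t(0.975, n−1) × SD / √n.

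- n = 3 (one planned cohort): 4.303 / √3 = 2.484 × SD.
- n = 6 (two cohorts pooled at one dose): 2.571 / √6 = 1.049 × SD.

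The documents give no SD of change. Assuming 12 ms, the half-widths are 29.8 ms (n = 3) and 12.6 ms (n = 6). Over an assumed range of 8 to 16 ms they are 19.9 to 39.7 ms and 8.4 to 16.8 ms.

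**The case against.** Several replies have force.

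- **The summary may be intended.** SAP 15.7 does refer to summary statistics, section 9 supplies default statistics by dose level, and section 18 says that table specifications are held in a separate document, which is not available here. A reader might infer that the SAP has replaced the protocol's analysis with a worst-value table. The documents do not show that; they show that the analysis is not specified. That still matters, because section 4 says the plan gives detailed specifications for all analyses.
- **The endpoint is served.** Protocol 8.3.2 concerns the occurrence of abnormal ECGs, which a frequency table addresses. This stands, but 8.5.4.3 plans the per-time-point summary as well.
- **The signs may be a reading error.** If the top categories lost an underline and were ≥500 and ≥60, the set would be complete and +60 ms would sit in the top group, in line with Protocol 7.2.6. The ≤480 nearby was read correctly, but that does not exclude this. If instead each < was meant as ≤, +60 ms would sit in the lower group.
- **Interruptions are visible elsewhere.** A reader might infer that a subject interrupted for QTc could go unseen. The documents do not support this. Clinically significant ECG abnormalities are recorded as adverse events (Protocol 7.2.6), events leading to M3541 interruption are tabulated and listed (SAP 15.2.2), and all ECG values are listed. The protocol's trigger also needs two consecutive ECGs without another explanation, which no single-worst-value table represents.
- **A mean shift would not necessarily be missed.** Protocol 7.4.4 and Table 4 plan a central quantitative analysis of triplicate-equivalent recordings time-linked to PK samples. The SAP does not describe its outputs, but the possibility of detection remains. At three subjects, individual curves may be as informative as a mean.

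**Conclusion.** The point holds as a minor reporting gap. Protocol 8.5.4.3 plans per-time-point ECG summaries with changes from baseline; SAP 15.7 specifies no such table, and SAP 7 does not declare a departure. The same table is absent for vital signs and ECOG, although the vital-signs listing does carry change from baseline.

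The category gaps are real as printed but confined to two exact values, 500 ms and +60 ms. Whether they exist in the source document depends on the inequality signs, which need checking there. Neither gap removes data from the listings or alters subject management. This conclusion assumes that the separate table specifications do not already supply the missing table; if they do, a cross-reference in 15.7 would settle that part.

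**What to change.** 1. Add to SAP 15.7 a table of observed value and change from baseline for the quantitative ECG parameters (heart rate, PR, RR, QRS, QT, QTcF) by dose level and by nominal time point from SAP Table 4, using the section 9 descriptive statistics.
2. Either add the corresponding tables for vital signs and ECOG or declare and justify their omission in SAP 7.
3. Confirm the inequality signs in 15.7 and make the reporting categories exhaustive: >450 to ≤480, >480 to ≤500 and >500 ms; >30 to <60 and ≥60 ms. The increase cut-point then agrees with the number in Protocol 7.2.6. This concerns reporting only and leaves the clinical rule as it is.

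The cost is SAP wording and one extra ECG table from data already collected, plus the vital-signs and ECOG tables if these are added rather than declared omitted. The downside is that the means will be imprecise with about 3 to 6 subjects per dose level, so the table should be read beside the individual plots.
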